Study Protocol

Comparison Between the Axillary Bilateral-breast Approach (ABBA) and Bilateral Axillo-breast Approach (BABA) for Robotic Thyroidectomy (NCT02768753) April 30,2017

Objective

To compare the therapeuic effcts between the axillary bilateral-breast approach (ABBA) and bilateral axillo-breast approach (BABA) for robotic thyroidectom. To explore the efficacy, safety, cosmetic results and clinical value by the two approaches

Criteria

Inclusion Criteria: The initial surgery;preoperative needle aspiration biopsy of thyroid cancer, and the diameter of no more than 1cm, no lateral neck lymph node metastasis;the tumor is confined to the thyroid membrane, not invading trachea and recurrent laryngeal nerve;intraoperative frozen section diagnosis of thyroid cancer;the patient informed consent.

Exclusion Criteria : High-frequency ultrasound preoperative tumor diameter greater than 1cm, or lateral neck lymph node metastasis in patients;there had been a history of thyroid surgery or neck radiation therapy;pregnant or lactating women;with severe Hashimoto's thyroiditis, thyroid volume greater than II°;coagulation disorders,hyperthyroidism or hypothyroidism patients;sternal goiter.

Methods

All patients were dived into two groups randomly. According to the standard of surgey, the 60 patients who have been diagnosed with thyroid cancer are numbered. The random number is even assigned ABBA group(n = 30) and the random number is odd assigned BABA (n = 30). All patients were operated on by the same surgical team through the da Vinci robotic surgical system use method of circular mobilization. After the operation, the number of resected lymph nodes, intraoperative blood loss, postoperative pain scores 24h, catheterization time, the time of drainage, Swallowing Evaluation , Subjective Voice , operative time, postoperative hospital stay, cosmetic results satisfaction, recurrent laryngeal nerve injury and hypoparathyroidism and other related complications were compared between groups. The patients were

followed up for 3~22 months.

Data management and statistical analysis:

SPSS 22.0.0 software was used for statistics. The measurement data were used to describe the average number of standard deviation; the ratio / rate of counting data was calculated; the measured data between the two groups were compared with the paired t test; the rate of the two groups was compared with the chi square test. The difference was statistically significant in p<0.05.

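### Does the even/odd random-number rule need changing because number generation, concealment and the order relative to frozen section are not described?

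*Combined protocol and SAP*

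**What the plan says.** The Methods section of the combined protocol and SAP states that allocation was random, "All patients were dived into two groups randomly", that "the 60 patients who have been diagnosed with thyroid cancer are numbered", and that the arm follows from parity: "The random number is even assigned ABBA group(n = 30) and the random number is odd assigned BABA (n = 30". It says no more on allocation. The source of the numbers, any blocking, the holder of the list and the way an assignment was revealed are not given, and blinding is not mentioned.

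The Criteria section requires both "preoperative needle aspiration biopsy of thyroid cancer" and "intraoperative frozen section diagnosis of thyroid cancer". The document does not say whether allocation came before or after the second of these, and it defines no analysis population.

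Of the 12 outcomes named in Methods, four are or appear to be ratings: "postoperative pain scores 24h", "Swallowing Evaluation , Subjective Voice" (two outcomes) and "cosmetic results satisfaction".

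**The concern.** Three things catch the eye.

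- **Parity with fixed arm sizes.** If each patient receives an independent random number, the arms are not fixed at 30 each. If the number is the patient's place in the enrolment order, parity is alternation and the next arm is known in advance.
- **No concealment.** If patients enter one at a time and the next assignment can be seen, those enrolling could steer patients towards an arm. No later safeguard is described that would reveal it.
- **An eligibility criterion met during surgery.** The arms are surgical approaches, so the frozen-section result would normally arrive after the approach is set. Allocated patients could then be dropped, and the plan has no rule for them.

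At stake is whether the two groups were comparable at entry, in a trial of 60 patients with several subjective outcomes.

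**Working it through.** **Inputs from the document:** 60 patients, 30 per arm, significance level 0.05. The document gives no SD, effect size, frozen-section failure rate or steering rate, so the values used for these below are assumptions.

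**1. Can the stated 30:30 arise?** Half of the numbers 1 to 60 are even, so a random permutation of them gives 30:30 with certainty. With independent random numbers:

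- P(30:30) = C(60,30)/2^60 = 0.103.
- Mean absolute difference in arm size = 60 × 0.1026 = 6.15.
- Mean efficiency relative to equal arms = E[4·n1·n2/60²] = (3600 − 60)/3600 = 0.983.

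The stated sizes therefore fit a legitimate method, or may simply be the realised counts. Imbalance alone causes no bias and costs under 2% in precision.

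**2. What if assignments were visible and patients were steered?** Suppose a share s of each arm is steered so that steered patients differ by d SD between arms. The bias is then s × d SD. Two-sided type I error of a two-sample t test at 30:30, from 100,000 simulated trials per setting:

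| Share steered (per arm) | d = 0.5: bias, error | d = 1.0: bias, error |
|---|---|---|
| 10% (3) | 0.05 SD, 5.5% | 0.10 SD, 6.5% |
| 20% (6) | 0.10 SD, 6.6% | 0.20 SD, 11.3% |
| 30% (9) | 0.15 SD, 8.6% | 0.30 SD, 19.3% |

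Hand check for s = 20%, d = 0.5: the standard error is √(2/30) = 0.258 SD and 0.10/0.258 = 0.39. So the error is about Φ(−1.96 + 0.39) + Φ(−1.96 − 0.39) = 0.058 + 0.009 = 0.067, in line with 6.6%. With s = 0 the error is 5%. Every departure from 5% comes from the assumed s and d.

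**3. Frozen section.** If a fraction q of 60 allocated patients fails it, 60q are excluded: 0.6, 1.8 or 3.0 patients for q = 1%, 3% or 5% (assumed). Let all of them come from one arm and differ by 0.5 SD from the rest of that arm. The bias is (60q/30) × 0.5 = 0.01, 0.03 or 0.05 SD. The largest is about a fifth of the standard error (0.05/0.258 = 0.19). If the criterion acts alike in both arms, the comparison is not biased.

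**4. Would another scheme be clearly better?** Suppose all past allocations are known and one always guesses the arm that is behind. The excess of correct guesses over chance in a balanced block of size 2m is (2^(2m)/C(2m,m) − 1)/2. One random ordering of 30 and 30 gives (1/0.1026 − 1)/2 = 4.4. Mixed blocks of 4, 6 and 8 give about 11.0 over 60 patients. Independent uncapped numbers give 0. Tighter balance is paid for in predictability.

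**The case for a change.** The strongest opposing argument is that silence on concealment cannot be read as concealment. Methods reports follow-up of 3 to 22 months. If follow-up closed on a common date, operations were spread over up to 22 − 3 = 19 months, which makes one-by-one enrolment plausible. A single team performed every operation and so knew past allocations. If the numbers followed entry order, the next arm would have been foreseeable.

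Part of this stands. The document does not establish that assignments were hidden, and a reader of the results needs to know. Three points limit it.

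- The text calls the number random. Reading it as entry order replaces what is written with something that is not.
- The wording also allows all 60 patients to have been assembled before numbering, which closes the steering route.
- The same follow-up range looks like a realised one. With the past tense for surgery and follow-up, it points to completed allocation, which new plan wording cannot alter.

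The rated outcomes and the lack of any mention of blinding do not strengthen the case. Concealment protects entry to the trial, not the scoring of pain, voice, swallowing or appearance.

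On frozen section, the 60 numbered patients are described as already diagnosed. That could mean the needle biopsy or the frozen section. If it means the latter, no allocated patient could fail it. The order is unsettled, so a count of exclusions by arm would be informative, but that is a reporting item.

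**Conclusion.** No change to the plan follows. The omissions are genuine, but the plan states random allocation, its 30:30 is attainable by a sound method, and nothing in it shows a visible or predictable list. Followed as written, it could yield a valid comparison.

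Imbalance costs 1.7% in mean efficiency at most, and nothing if a permutation was used. The frozen-section effect is at most 0.05 SD, assuming 5% failures, all in one arm, differing by 0.5 SD. The type I error figures of 5.5% to 19.3% rest wholly on assumed sequential entry, a visible list and deliberate or unconscious steering. They illustrate a possibility and do not measure this trial.

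If allocation is complete, as the text suggests but does not prove, a new randomisation scheme is moot. The authors can give the generation method, the concealment and the numbers allocated and excluded by arm in the trial report, and should call 30:30 fixed only if the method fixed it. If some allocation remains, the existing rule can be run from a concealed, pre-generated list without contradicting anything in the plan. Choosing blocks or a single ordering instead is a trade-off between balance over time and predictability, with no clear gain.

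### One team performs all 60 operations and the analysis ignores case order; any improvement over the series would cost precision, which a case-sequence term would largely recover at little cost

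*Combined protocol and SAP*

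**What the plan says.** The Methods put every operation with one team on one platform: "All patients were operated on by the same surgical team through the da Vinci robotic surgical system use method of circular mobilization". On allocation they say that "the 60 patients who have been diagnosed with thyroid cancer are numbered" and then that "The random number is even assigned ABBA group(n = 30) and the random number is odd assigned BABA (n = 30". No block, stratum or calendar period is mentioned. Patients were "followed up for 3~22 months".

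Under data management and statistical analysis, "the measured data between the two groups were compared with the paired t test", and for proportions "the rate of the two groups was compared with the chi square test". The threshold is given as "The difference was statistically significant in p<0.05". No covariate, period or case-order term appears, and no pairing is defined. The documents do not mention a learning curve, the order of operations, or how many procedures of either kind the team had done before the trial.

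**The concern.** Using a single team removes differences between operators, but it places all 60 cases on one team's experience curve. That the cases were done one after another is an inference from there being one team. If all patients share one follow-up cut-off, which is not stated, operations were spread over about 22 - 3 = 19 months.

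If the team became quicker or more proficient over that time, two things would follow. The trend would widen the spread within each arm and reduce power. The arms could also differ by chance in how many early cases they hold, which would move the single estimate the trial reports. Operative time, blood loss and number of nodes removed are the listed outcomes where this seems most plausible. That is a judgement; the documents do not say so.

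**Working it through.** **Inputs.** From the documents: 60 patients, 30 per arm, one team, significance at 0.05. Assumed: two-sided testing; residual SD of 1; an improvement common to both arms totalling L residual SDs from case 1 to case 60, with L from 0 to 2, linear or exponential (15-case constant).

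**1. The plan's own figure.** The 60 cannot be reproduced, because no effect size, SD or power is stated. Working backwards, 30 per arm detects (1.960 + 0.842) × √(2/30) = 0.72 SD with 80% power (normal approximation). A true difference of 0.736 SD gives about 80% with a t test and serves as the reference case.

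**2. Chance imbalance in case order.** The variance of case numbers 1 to 60 is 60 × 61/12 = 305. Under unblocked random 30:30 allocation, the difference in mean case number has variance 305 × 2/30 = 20.3, so SD 4.51 cases. The arms differ by 5 or more cases in about 27% of allocations.

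**3. What that does to the estimate.** A linear trend is L/59 per case. The shift in the arm difference therefore has mean 0 and SD 4.51 × L/59 = 0.076 L. At L = 1, 95% of shifts are below 0.15 SD in size; at L = 2, below 0.30 SD.

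**4. What it does to precision.** The trend adds variance 305 × L²/59² = 0.088 L². The SD is multiplied by √1.088 = 1.043 at L = 1 and √1.350 = 1.162 at L = 2. In the normal approximation with 80% power at L = 0, power becomes Φ(2.802/1.043 - 1.960) = 76.6% and Φ(2.802/1.162 - 1.960) = 67.4%.

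**5. Simulation.** 10,000 trials per scenario, true difference 0.736 SD, unblocked 30:30 (Monte Carlo standard error about 0.4 to 0.5 points):

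| Learning | Unpaired t test | Arm + linear case order |
|---|---|---|
| None | 80.5% | 79.7% |
| Linear, 0.5 SD | 79.5% | 80.1% |
| Linear, 1 SD | 77.5% | 80.1% |
| Linear, 1.5 SD | 72.2% | 78.8% |
| Linear, 2 SD | 68.0% | 80.2% |
| Exponential, 1 SD | 77.1% | 78.8% |
| Exponential, 2 SD | 69.5% | 77.4% |

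A separate run of 4,000 trials per scenario gave 77% and 67% unadjusted at 1 and 2 SD of linear learning. With no true difference, the type I error of the unpaired test stayed at 4.7-5.5%.

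**6. The other reading of the allocation.** Independent parity draws give exactly 30:30 with probability C(60,30)/2^60 = 10.3%, so some unstated constraint may apply. If parity is that of the enrolment number, the arms alternate and their mean case numbers differ by 1. The shift is then L/59, about 0.03 SD at L = 2, and steps 2 and 3 do not apply.

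**7. Blocking.** Blocks of 4 cut the SD of the shift at L = 1 from 0.077 to 0.006. Unadjusted power remains 76.6% at 1 SD and 69.2% at 2 SD. Adding case order brings it to 79.3% and 79.5%.

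**8. Can 60 cases show whether a difference persists?** Splitting at case 30 leaves about 15 per arm per half. At 80% power, the detectable difference within a half is 2.802 × √(2/15) = 1.02 SD, and the detectable change between halves is 2.802 × √(4/15) = 1.45 SD.

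**The case against.** The strongest reply is that nothing in the documents shows any learning. A team already settled in both approaches fits the text equally well, and then there is nothing to correct. Even at 1 SD of improvement the loss is only about 3 points of power, and the 80% baseline is itself assumed. This stands: the size is conditional, and the loss becomes material only at about 1.5 to 2 SD.

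A reader might infer that team learning biases the ABBA-BABA difference. The documents do not support that. With random allocation and learning common to both arms, the expected shift is zero, and its chance variation is already within the standard error of an unpaired test.

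The power figures describe an unpaired test, whereas the plan names a paired one. This also stands. With no pairing defined, the stated test cannot be evaluated as written. If the k-th case of one arm were paired with the k-th of the other, type I error would rise to 5.8% at 1 SD and 9.4% at 2 SD of linear learning. That comes from the undefined pairing, which is a defect in its own right.

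Finally, the linear case-order term does best when the true trend is linear. It recovers somewhat less under exponential learning (77.4% at 2 SD), so full recovery should not be promised.

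**Conclusion.** The point holds as a matter of precision. One team does every case, and neither the described allocation nor the described analysis uses case order. For a comparison with about 80% power, leaving out case order costs nothing if there is no learning, about 3 points at 1 SD of linear improvement and about 12 points at 2 SD. A case-order term keeps power at about 77-80%. These figures rest on an assumed learning size, learning common to both arms, two-sided 0.05 and an unpaired test. The chance-imbalance figures also need unblocked random allocation, which the text does not settle.

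A reader might go further and infer that the team was still learning one approach, so that a difference would reflect familiarity and not the approach. Randomisation would not remove such an effect: if one arm's deficit fell linearly from L to 0, the average difference would be L/2. But the documents say nothing about experience with either approach, so this remains an open question to be met by reporting prior case counts. Adding case order as a main effect would not resolve it, and 60 cases are too few to establish whether a difference persists.

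**What to change.** - Compare operative time, blood loss and node count with an independent-groups linear model containing arm and the team's case sequence number, derived from the operation date. This replaces the stated paired t test for these outcomes.
- Report the arm-by-sequence term with its confidence interval, labelled exploratory, and draw no conclusion about persistence from it.
- Report how many ABBA and BABA operations the team had done before the first trial case.
- State how the random numbers were generated and whether parity refers to a random number or to the enrolment number.
- Use randomly permuted, concealed blocks only if allocation is still open; the past tense of the Methods suggests it may not be. Blocks even out timing but do not restore power without the case-order term.

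The cost is one derived covariate and one degree of freedom for the main model (about 1 point of power if there is no learning), one more degree of freedom for the exploratory interaction, and a sentence on prior experience.

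### Extent of resection is neither fixed nor recorded, and node count, operative time and blood loss are compared unadjusted; if extent varies, the cost is mainly lost precision and chance imbalance

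*Combined protocol and SAP*

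**What the plan says.** Eligibility (Criteria) is defined by tumour and patient features. It requires "preoperative needle aspiration biopsy of thyroid cancer, and the diameter of no more than 1cm, no lateral neck lymph node metastasis", and also that "the tumor is confined to the thyroid membrane, not invading trachea and recurrent laryngeal nerve", with confirmation by "intraoperative frozen section diagnosis of thyroid cancer". Neither the inclusion nor the exclusion list says whether the thyroidectomy is one- or two-sided, or whether central node clearance is.

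The Methods section standardises some features of the surgery: "All patients were operated on by the same surgical team through the da Vinci robotic surgical system use method of circular mobilization". Extent of resection is not among them, and it is not listed as a variable to be recorded. A passing reference to a surgical standard is too vague to read as a rule on extent.

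Allocation is by parity of a random number, with no stratification factor: "The random number is even assigned ABBA group(n = 30) and the random number is odd assigned BABA (n = 30".

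The compared outcomes include "the number of resected lymph nodes, intraoperative blood loss, postoperative pain scores 24h, catheterization time". Operative time is compared as well, and the list ends with "recurrent laryngeal nerve injury and hypoparathyroidism and other related complications were compared between groups". The section on data management and statistical analysis plans a t test for measurements (described as paired) and a chi-square test for rates, both without a covariate or stratum.

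**The concern.** As written, one-sided and two-sided operations both fit the plan. A two-sided clearance takes in more node-bearing tissue, a larger resection can be expected to take longer and bleed more, and a one-sided resection leaves the opposite nerve and parathyroid glands untouched. These links are anatomical reasoning. The documents do not state them, and the size of the effect is not known from the documents.

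If extent varies among the 60 patients, two things follow for node count, operative time and blood loss. The variation due to extent is added to the error term, so a given approach effect is harder to detect. In a trial of 30 per arm, the arms may also end up with visibly different mixes of extent by chance. With no record of extent, the report could neither show nor correct this.

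**Working it through.** **The plan's own figure.** The sample size is 60 ("the 60 patients who have been diagnosed with thyroid cancer are numbered"), 30 per arm. It cannot be reproduced, because no effect size, SD, event rate or power is given. For orientation, the difference detectable with 80% power at two-sided 5% is (1.960 + 0.842) × √(2/30) = 0.723 SD. The plan does not state sidedness; two-sided is assumed.

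**Assumptions, none of them from the documents.**
- q, the share with two-sided surgery: 30% or 50%.
- D, the shift in outcome due to two-sided surgery: 1, 1.5 or 2 within-extent SD.
- True approach effect: 0.75 SD, close to the detectable difference above.
- Test: two-sample t, because the arms are independent groups. The figures do not describe a paired test.

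**Step 1, crude power.** With extent in the error term, SD = √(1 + q(1 − q)D²). Power is from the noncentral t distribution with 58 degrees of freedom and noncentrality (0.75/SD) × √(30/2).

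| q | D | SD | Effect in crude SD | Power |
|---|---|---|---|---|
| any | 0 | 1.000 | 0.750 | 81% |
| 30% | 1 | 1.100 | 0.682 | 74% |
| 30% | 1.5 | 1.213 | 0.618 | 65% |
| 30% | 2 | 1.356 | 0.553 | 56% |
| 50% | 1 | 1.118 | 0.671 | 72% |
| 50% | 1.5 | 1.250 | 0.600 | 63% |
| 50% | 2 | 1.414 | 0.530 | 52% |

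**Step 2, adjusted power.** A term for planned extent returns the residual SD to 1 and uses one degree of freedom (57 left). Simulated power is 80% to 81% in all these settings. If extent has no effect, the term costs about 1 point of power or less.

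**Step 3, chance imbalance.** A gap of 20 percentage points is 6 patients in 30. The probability of a gap that large or larger depends on the sampling model:
- each patient's extent independent: 12% (q = 30%) and 15.5% (q = 50%);
- totals fixed at 18 or 30 of 60 (hypergeometric): 16% and 20%.

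Such a gap moves the crude difference by 0.2 × D, that is 0.2 SD at D = 1 and 0.4 SD at D = 2.

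**Step 4, error rate.** When extent does not depend on the arm, the simulated type I error of the unadjusted unpaired t test at q = 50% is 4.8%, for D = 1 and for D = 2. Chance imbalance is therefore already allowed for in the p-value.

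**Step 5, hypoparathyroidism.** Suppose half the patients are one-sided and at no risk, and the risks among the rest are 30% and 10%. The overall risks are then 15% and 5%. Exact power of the uncorrected chi-square test is 26% with all 30 per arm and 28% with only the 15 at-risk patients per arm. Restricting the table gains almost nothing at these rates.

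**The case against.** **Randomisation already handles this.** For extent planned before allocation this stands: balance holds in expectation and the error rate stays near 5%. What remains is the precision that an adjusted analysis would recover.

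**Extent may not vary.** Tumours are limited to 1 cm, confined to the gland and without lateral nodes, at initial surgery under one team. A single standard operation is possible. The plan does not say so, and if it is the case, one sentence settles the point. The mix and effect sizes above are assumptions, and 52% is their most adverse corner; at D = 1 the loss is 7 to 9 points.

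**A stronger reading is tempting.** A reader might infer that differences between the arms would reflect how much was removed rather than the route, because the team cannot be blinded to the route and might remove more through one than the other. If extent did diverge by 20 points after allocation (simulated around a 50% mix), the crude test would reject in about 11% (D = 1) or 19% (D = 2) of trials with no approach effect at a given extent. But nothing in the documents says that removal differs by route. If it did, the difference would be a consequence of the approach and part of its total effect on node count, not confounding. Adjusting for planned extent would not remove it.

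**The remedy may come late.** Final extent may depend on the frozen section, and the Methods are written largely in the past tense. The first point is a reason to record the plan separately from what was done. The second may limit what can still be recorded before allocation.

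**Conclusion.** The omission is real: extent is not fixed, not recorded, not stratified and not adjusted for. The documents support a finding of lost precision and possible chance imbalance, conditional on extent varying. They do not support a finding of systematic bias. Under the stated assumptions, power for a 0.75 SD effect falls from about 81% to between 74% and 52%, adjustment brings it back to about 80%, and a 20-point imbalance occurs in about 12% to 20% of trials, depending on the mix and the sampling model. For hypoparathyroidism, one-sided operations would lower the absolute rates without biasing the comparison. The sponsor should act on the point because the remedy is cheap, but it does not invalidate the comparison.

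**What to change.** - Record planned extent (one- or two-sided thyroidectomy, one- or two-sided central clearance) before the random number is read.
- Compare node count, operative time and blood loss with an unpaired linear model containing arm and planned extent. Do not adjust for actual extent, which the arm may affect.
- Tabulate planned against actual extent by arm, so that any divergence after allocation is visible. Report such a divergence as part of the approach's total effect.
- Report hypoparathyroidism overall and, descriptively only, among patients planned for two-sided resection.
- If every patient has the same operation, say so; the term then drops out.

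The cost is one preoperative entry and one degree of freedom, about 1 point of power or less if extent has no effect. The additional hypoparathyroidism table has a smaller denominator. If allocation is already complete, only a plan documented before it can serve as the covariate; otherwise the tabulation of actual extent by arm is what remains. None of this takes a view on which extent of surgery is right.

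### Does the lack of a fixed assessment time for swallowing, voice, cosmetic satisfaction, nerve injury and hypoparathyroidism undermine their comparison when follow-up runs from 3 to 22 months?

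*Combined protocol and SAP*

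**What the plan says.** The document is short, and one sentence in Methods carries the whole outcome list. It opens "After the operation, the number of resected lymph nodes, intraoperative blood loss, postoperative pain scores 24h", so the only general timing is that the outcomes come after surgery. Pain is the one item with a clock time: "postoperative pain scores 24h". The list continues through "Swallowing Evaluation , Subjective Voice , operative time, postoperative hospital stay" and ends with "cosmetic results satisfaction, recurrent laryngeal nerve injury and hypoparathyroidism and other related complications were compared between groups". A separate sentence then says the patients were "followed up for 3~22 months". There is no visit schedule.

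Under Data management and statistical analysis, measurements are compared with a t test (described as paired), and "the rate of the two groups was compared with the chi square test". Neither analysis has a term for time since surgery or length of follow-up.

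**The concern.** Voice, swallowing, satisfaction with a scar, nerve function and parathyroid function can all change in the months after thyroid surgery. If each patient's reading came from the last visit, one patient's score could date from month 3 and another's from month 22. The mean would then describe no particular time. A complication rate could likewise mean either any event or an event still present, and a reader could not separate transient from lasting injury.

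These outcomes matter to the trial. The Objective names safety and cosmetic results. Satisfaction is the only cosmetic measure listed, and nerve injury and hypoparathyroidism are the only complications named. The planned tests ignore time, so they could not repair mixed readings. With 30 patients per arm, extra variance is unwelcome.

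**Working it through.** **1. Which outcomes lack a time.** Methods names 12 specific outcomes.

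- Seven are anchored to the operation, the admission or a stated hour: node count, blood loss, pain at 24 h, catheterization time, drainage time, operative time and hospital stay.
- Five are not: swallowing, voice, cosmetic satisfaction, recurrent laryngeal nerve injury and hypoparathyroidism. The unnamed other complications share the gap.

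**2. Does the text say that readings were mixed?** It does not. The outcome list hangs on the phrase about the period after the operation. The follow-up range stands in its own later sentence, and nothing says that any outcome was read at the end of follow-up. Two readings fit: one common early assessment, or a last-visit assessment.

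**3. Does mixed timing bias the test?** Let a score be Y = arm effect + drift × (T − 3)/19 + error, with T the month of reading. If T has the same distribution in both arms, as randomisation makes it in expectation, the drift term has the same mean in each arm and cancels from the difference. Only the variance grows. In 40,000 simulated trials with uniform follow-up, the two-sided 0.05 test rejected a true null at 0.050 (drift 1 SD) and 0.049 (drift 2 SD). Bias would need follow-up that differs by arm, and the document gives no follow-up by arm.

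**4. How much precision could be lost?** The plan states no power, effect size, SD or event rate, so there is no figure of its own to reproduce. From the document: 30 per arm, α = 0.05 (taken as two-sided), T between 3 and 22. Assumed: continuous scores, an unpaired t test because the arms contain different patients, 80% power as a benchmark, and the drift and the distribution of T.

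- Detectable difference: 30 per arm and 80% power give d = 0.736 SD.
- SD inflation: √(1 + drift² × Var(T)/19²).
- Var(T): uniform, 19²/12 = 30.1; half the patients at each end, 9.5² = 90.25; 58 patients at 12.5 months and one at each end, 2 × 9.5²/60 = 3.01.

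| Drift over 19 months | Uniform | Half at each end | Nearly all mid-range |
|---|---|---|---|
| 0.25 SD | 79.8% | 79.4% | 80.0% |
| 0.5 SD | 79.2% | 77.6% | 79.9% |
| 1 SD | 76.8% | 70.7% | 79.7% |
| 2 SD | 68.0% | 50.9% | 78.7% |

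Worked case: 1 SD drift with uniform follow-up gives √(1 + 30.1/361) = 1.041, so the effect shrinks to 0.736/1.041 = 0.707 SD and power to 76.8%.

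**5. How far could the meaning of a rate move?** If complications resolved with half-life h months, the share still present at month m is 0.5^(m/h). For h = 3 this is 50% at 3 months and 0.6% at 22; for h = 12 it is 84% and 28%. The half-lives are assumptions. The calculation shows that the two definitions can differ widely, not that this trial mixed them.

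**6. How unequal is follow-up?** Uniform follow-up would put 3/19 = 16% of patients under 6 months. A triangular distribution peaking at 3 months gives 1 − (16/19)² = 29%; one peaking at 22 months gives (3/19)² = 2%. The stated limits alone allow anything from 1 to 59 of the 60 patients.

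**The case for a change.** The strongest case for a change does not depend on power. A complication rate with no time and no persistence rule cannot be interpreted whatever its p-value. The authors did fix a time for pain in the same sentence, so they could have done so here. Three months is the latest time every patient reaches under the stated follow-up, so a common assessment then would lose nobody.

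Part of this stands. The omission is genuine, it is not explained by redaction or PDF reading, and the trial report should say when each outcome was read.

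The step to a prescribed rule does not stand:

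- Any common time before 3 months also loses nobody, and one time for five different outcomes is a preference.
- The rule needs dated readings near 3 months, which the document does not confirm.
- The document is written partly in the past tense. If data are already in hand, choosing a time now could add a post hoc choice unless it is made without sight of results by arm.
- Adjusting scores for time since surgery could serve as a fallback, but it gives the complication rates no rule.
- No scale is named for swallowing, voice or satisfaction, so a common date alone would not give those scores a common meaning.

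**Conclusion.** The concern identifies a missing detail, not a rule that gives a wrong result, and no change to the plan follows. Type I error is unaffected so long as timing does not differ by arm, and no such difference is shown.

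The loss of precision cannot be quantified from the document. Under uniform follow-up it is under 1 percentage point of power for a drift of up to 0.5 SD and about 3 points at 1 SD. The fall to 51% needs both a 2 SD drift and half the patients at each extreme. All of these figures assume continuous scores read at the last visit, which the text does not say.

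What is left is a matter of definition and reporting that competent analysts settle as routine: state the actual assessment time of each outcome, including the unnamed complications; separate any occurrence from persistence where dated readings exist; and give follow-up by arm. The judgement would change if the readings proved to come from the last visit and follow-up differed materially between arms.
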